1 BACKGROUND INFORMATION AND RATIONALE

A.1. Impact of the Condition on the Health of Individuals and Populations

[figure not shown]
A.a.1. Impact of maternal depression during pregnancy

More than 20% of pregnant women may have a depressive disorder or symptoms during pregnancy¹⁻³. However, it is well-recognized that depression during pregnancy is significantly underappreciated and under-recognized, thus under-diagnosed^{1,4-9}. While there have been no good data on the degree of under-diagnosis of depression during pregnancy, one of the studies conducted in the Kaiser Permanente Northern California (KPNC) population suggested a detection rate of only 37% for postpartum depression¹⁰. This detection rate is comparable to that reported in the literature¹¹⁻¹³. Various studies including a study conducted by the Principal Investigator among the KPNC population have shown that prenatal depression is likely to affect about 20% of pregnant women^{3,9,14-16}. Therefore, depression during pregnancy is prevalent and has significant clinical and public health importance. Emerging evidence has shown that depression in pregnancy increases the risk of preterm delivery (PTD) and low birthweight (LBW).

A.a.2. Impact of PTD and LBW

PTD, defined as birth before 37 completed weeks of gestation, is the leading cause of perinatal mortality and morbidity. It accounts for about 30% of early neonatal deaths worldwide^{17,18}. It is also the leading cause of congenital neurological disabilities including cerebral palsy, blindness and deafness and learning disability in the U.S. and most developed countries¹⁹⁻²². In addition, it is the major cause of admission to the neonatal intensive care unit and a significant contributor to medical expenditure for infants. The costs associated with PTD amount to more than \$26 billion each year²³⁻²⁵. Such impact on infant health and on staggering medical and economic costs makes PTD one of the most serious challenges for clinicians and biomedical researchers today and has become a global crisis^{26,27}. Thus, reducing PTD and LBW could lead to a significant reduction in medical care costs and to improved newborn health. However, despite decades of research, the incidence of PTD has not been reduced; instead, it has been steadily increasing^{20,28-30}. In the US, about 12% of all births (>half a million births) are the result of PTD each year.

Figure 1. Potential mechanistic pathways between depression and adverse pregnancy outcomes

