3.1.2 Choice of outcomes

PTD, defined as birth before 37 completed weeks of gestation, is the leading cause of perinatal mortality and morbidity as well as a leading cause of congenital neurological disabilities including cerebral palsy, blindness and deafness in the U.S. and most developed countries¹⁹⁻²². In addition, it is the major cause of admission to the neonatal intensive care unit and a significant contributor to medical expenditure for infants, amounting to more than \$26 billion each year²³⁻²⁵. Such impact on infant health and on staggering medical and economic costs makes prematurity one of the most serious challenges for clinicians and researchers today and has become a global crisis according to WHO reports and March of Dimes White Paper^{26, 27}. Patients with premature infants have severe physical, emotional, and financial burdens beginning at delivery. Premature birth turns a happy event (having a new child) into a nightmare. Risk factors for prematurity are largely unknown, thus there has not been much progress in reducing premature births largely due to a lack of intervention strategy, which leaves pregnant women to face significant uncertainty throughout pregnancy. Given depression in pregnancy has emerged as an important and potentially modifiable risk factor for prematurity, identifying an effective treatment option for pregnant women with varying type and severity of underlying depression could prove a valuable intervention strategy to reduce prematurity, which could be a significant contribution and help for pregnant women and society in general.

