Outcomes (PTD & LBW): Gestational age at delivery is determined by obstetricians based on multiple sources including ultrasound dating, physical examination, and LMP. Birthweight is measured by medical practitioners at delivery. This information is recorded in the KPNC EMR. In several studies conducted by the PI, more than 99% of participants had reliable information on gestational age and birthweight at delivery in the KPNC EMR. For the remaining <1% that may have delivered outside KPNC hospitals, we are also able to obtain information through searching various databases including outside payment service databases. In addition, KPNC has a well-established Neonatal Minimum Data Set which verifies all NICU admissions for diagnosis and treatments. This database allows ascertainment of information on gestational age and birthweight for deliveries with missing information. We will also ascertain other related information such as indications for PTD and other pregnancy or labor complications for further classification of PTD. A sample of PTD and LBW records will be selected and verified by manual review of medical records for quality control.

Potential confounders. In the stage-two subsample, we will conduct a structured telephone interview to ascertain detailed information on potential confounders that may not be available from the KPNC EMR. The focus will be known and suspected risk factors for PTD and LBW, personal and family history of mental illness, demographic, reproductive and psychosocial factors (e.g., social and family support that may be related to depression, PTD, and LBW), BMI, diseases during the index pregnancy (e.g., GDM), diet, lifetime and prenatal smoking. The PI and his research team have extensive experience ascertaining information on these variables for many of his previous NIH-funded studies. Questionnaires with these questions have been used in many previous

studies. Based on our experience conducting telephone interviews with KPNC pregnant women, a response rate of 80-85% is expected.

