4.1 Study Population

4.1.1 Inclusion Criteria

- 1) Females \geq age 18
- 2) Kaiser members
- 3) Pregnant beyond 20 weeks of gestation during the recruitment period
- 4) Meeting the definition of one of the following nine cohorts:

Cohort A (depression only): pregnant women who are depressed and use only antidepressants

Cohort A (depression with comorbidity): pregnant women who are depressed and use only antidepressants

Cohort B (depression only): pregnant women who are depressed and receive psychotherapy only

Cohort B (depression with comorbidity): pregnant women who are depressed and receive psychotherapy only

Cohort C (depression only): pregnant women who are depressed and receive antidepressants and psychotherapy

Cohort C (depression with comorbidity): pregnant women who are depressed and receive antidepressants and psychotherapy

Cohort D (depression only): pregnant women who are depressed and receive no treatment

Cohort D (depression with comorbidity): pregnant women who are depressed and receive no treatment

Cohort E: pregnant women who are not depressed (screen negative) and receive no treatment

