6 ANALYTIC METHODS

6.1 General Approach to Analyses

While all eligible pregnant women will be included in the registry after their pregnancies are identified, the follow-up time for all pregnancy outcomes of interest will start at 20 weeks of gestation because, by definition, PTD and LBW among live births occur after 20 weeks of gestation. All pregnancies ending before 37 completed weeks (259 days) will be considered as failure (PTD). As in our previous studies, we will use the Cox proportional hazards regression model, accommodating delayed entry into the cohort^{76,77}. Birthweight for all newborns will be obtained from EMR and analyses for LBW will utilize logistic regression.

The study design can be characterized as two-stage. Unlike typical applications of two-stage sampling in epidemiologic studies, where the stage-two sample is selected on the basis of both exposure (or exposure surrogate) and outcome (e.g. two-stage case-control sampling), only exposure status will be known at the time of stage-two sampling to keep the nature of a cohort study design. However, study outcomes of interest will eventually be measured on all 88,000 stage-one units, and there is much to be gained by utilizing all available information in estimation of associations of interest (see Sample Size and Statistical Power section).

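### Read literally, the PTD event rule counts every pregnancy that ends between 20 and 37 weeks, including terminations and stillbirths, and no other section limits it

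*Combined protocol and SAP*

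**What the plan says.** Section 6.1 sets time zero for every outcome: "the follow-up time for all pregnancy outcomes of interest will start at 20 weeks of gestation". The reason given is that "by definition, PTD and LBW among live births occur after 20 weeks of gestation". The next sentence is the event rule for the Cox model: "All pregnancies ending before 37 completed weeks (259 days) will be considered as failure (PTD". Its subject is pregnancies that end, not births.

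The outcome is defined elsewhere in narrower terms. Section 3.1.2 has "PTD, defined as birth before 37 completed weeks of gestation", and Section 1 (A.a.2) uses the same definition.

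Eligibility in Section 4.1.1 asks for "Pregnant beyond 20 weeks of gestation during the recruitment period" and does not require a live birth. On ascertainment, Section 3.1.3 says "Gestational age at delivery is determined by obstetricians based on multiple sources including ultrasound dating, physical examination, and LMP". It also plans to collect indications for PTD and labour complications so that PTD can be classified further, but it does not name vital status at delivery. The plan mentions neither stillbirth, fetal death nor termination, and it has no exclusion, censoring or competing-event rule for them.

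**The concern.** An analyst who programs the Cox model from Section 6.1 would code any ending from 20 weeks to before 259 days as a failure. Terminations and fetal deaths can relate to depression, psychiatric comorbidity or medication for reasons unrelated to preterm labour. Counting them mixes a different outcome into a hazard ratio that will be reported as an effect on preterm delivery.

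The mixing need not be equal across cohorts. Section 5 requires Cohort E to screen negative at both visits, and Section 3.1.3 puts the second screen at 22–24 weeks. A pregnancy that ends at 21 weeks cannot meet that definition, whereas a woman who was positive at the first screen and untreated can still be in Cohort D. This cohort-timing problem is a separate matter and also affects very early live births. It does show how early non-live endings, once counted, could fall unevenly.

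If the mixing is unequal, the resulting bias does not shrink as the 88,000 stage-one outcomes add precision.

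**Working it through.** **1. The plan's own figure.** Section 6.2.2 gives minimum detectable hazard ratios (HRs) for PTD of 1.69 to 1.83, for 400 versus 400 women, PTD rate 11% to 8%, two-sided α = 0.05 and power 0.80. With Schoenfeld's formula, the required events are 4(1.960 + 0.842)²/(ln HR)². The expected events are 400·[p + 1 − (1 − p)^HR], where p is the reference-group rate.

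| Reference rate p | Events at solution | HR, recomputed | HR, plan |
|---|---|---|---|
| 8% | 88.2 | 1.816 | 1.83 |
| 11% | 115.3 | 1.685 | 1.69 |

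With 1,600 per group the formula gives 1.380 and 1.321, against 1.38 and 1.32 in the plan. The figures reproduce and are not in dispute. They do not show whether the 8% to 11% is limited to live births.

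**2. Share of counted events.** Let p be the rate of preterm live birth, 0.08 to 0.11 (Section 6.2.2). Let x be the proportion of pregnancies that reach 20 weeks and end before 37 weeks without a live birth. The documents do not give x, and 0.2% to 1.5% is assumed. The share is x/(x + p).

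- Lowest: 0.002/(0.002 + 0.11) = 0.018.
- At x = 0.5%: 0.005/0.115 = 0.043 to 0.005/0.085 = 0.059.
- Highest: 0.015/(0.015 + 0.08) = 0.158.

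This is about 2% to 16% of counted events. In numbers, it is 176 to 1,320 among 88,000 women (88,000·x), or 0.8 to 6 in a cohort of 400 (400·x).

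**3. Shift in the hazard ratio.** Suppose preterm live births are equally frequent in two cohorts and the other endings are twice as frequent in one. Treating the HR as a ratio of risks, the factor is (p + 2x)/(p + x).

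| | x = 0.5% | x = 1% |
|---|---|---|
| p = 11% | 0.120/0.115 = 1.043 | 0.130/0.120 = 1.083 |
| p = 8% | 0.090/0.085 = 1.059 | 0.100/0.090 = 1.111 |

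If the excess lies in the reference cohort, the factor inverts, to between 1/1.043 = 0.96 and 1/1.111 = 0.90. If x is the same proportion in both cohorts and the true PTD ratio is 1, there is no shift.

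**4. Scale against the plan's targets.** Compare on the log scale with the two-stage detectable HRs of 1.32 (11%) and 1.38 (8%). The smallest case is ln 1.043/ln 1.32 = 0.15 and the largest is ln 1.111/ln 1.38 = 0.33. The shift is therefore 15% to 33% of the smallest effect that the two-stage calculation is meant to detect.

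**5. Cost of restricting to live births.** If the stated 8% to 11% already includes the other endings, the rate for live births is p − x. Solving step 1 again for 400 per group, with x from 0.2% to 1.5%, gives a detectable HR of 1.83 to 1.92 (from 1.816) at 8% and 1.69 to 1.74 (from 1.685) at 11%.

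**The case against.** The strongest reply is that the context points to births. The clause before the rule speaks of live births, Section 3.1.3 records gestational age at delivery, Section 7.1.1 refers to birth outcomes, and Section 7.5.3 links mothers to infants. The rule may be no more than a loosely worded statement of the 259-day cut-off. That is a fair reading of intent, and a reader should not infer that the plan deliberately chose an all-endings event. It does not settle the point, because the sentence that will be programmed omits the limit and nothing else supplies it.

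Second, a reader might infer that counting stillbirths contradicts the definition in Sections 1 and 3.1.2. The documents do not support that. Those sections say birth, not live birth, so the contradiction with them is clear only for terminations. For stillbirths the conflict is with the live-birth clause in Section 6.1.

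Third, a reader might treat the LBW analysis as a second inconsistency, since it uses newborns. Different analysis sets for different outcomes are not an error in themselves. Nor do the documents say when in pregnancy these endings occur, so a claim that they cluster in the earliest weeks has no support.

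Fourth, the aims concern fetal risk, and fetal death before 37 weeks could reasonably be part of a composite outcome. Censoring it could hide a harm of treatment. This objection stands, and it shapes the fix.

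Last, the classification by indication in Section 3.1.3 offers a partial way to separate some endings. However, it sub-classifies events already counted as PTD and does not name vital status.

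**Conclusion.** The concern holds in a limited form. As written, the event rule makes terminations after 20 weeks PTD events, against the plan's definition of PTD as a birth. It also counts stillbirths, against the live-birth wording beside it. This is a stated rule that gives the wrong event when followed, even if the cause is loose drafting.

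The likely effect is small to moderate: about 2% to 16% of counted events, and a factor of about 1.04 to 1.11 in the HR if a 0.5% to 1% rate doubles in one cohort. Both ranges rest wholly on assumed rates and an assumed doubling. The direction depends on which cohort has the excess. A reader might infer that the PTD results would be materially wrong, but the documents do not show that. They give no rate of these endings, overall or by cohort. The shift is also smaller than any effect the plan is powered to detect. The change is worth making because it is cheap and must be settled before outcomes are coded.

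**What to change.** Replace the sentence in Section 6.1 so that a PTD event is a live birth before 259 days. State that terminations and fetal deaths after 20 weeks are censored at their date and not counted as PTD, so that the HR is a cause-specific hazard ratio for preterm live birth. Add vital status and type of ending to the outcome data in Section 3.1.3.

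Because censoring fetal deaths could conceal a harm, report terminations and stillbirths by cohort. Add two sensitivity analyses: one that counts stillbirths before 259 days as failures, and one that counts all endings.

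The cost is a short change of text, one EMR flag and two extra model runs. The drawbacks are slightly fewer events (step 5 of the working) and a primary HR that no longer reflects fetal death, which is why the by-cohort report and the sensitivity analyses are needed.

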We will also examine the possible dose-response in the association between antidepressant use and PTD by examining dosage of use, duration of the use, and timing of effect (single vs. multiple trimesters), in the context of time-dependent covariates. Similarly, we will also assess any dose-response relationship in the association between psychotherapy and PTD (the number of sessions received) and the effect of timing of treatment, also both as time-dependent covariates. If sample sizes allow, we will also examine the effect of combination of dose and timing (e.g., dose-response during early and late pregnancy). In addition, we will examine difference in the type of antidepressants (SSRI vs. non-SSRI).

Analyses of LBW as the outcome will parallel those described above for PTD, but logistic regression techniques will be used rather than Cox regression.

Aim 2. Head-to-head comparison of treatment regimens among Cohorts A, B & C, respectively

We will obtain point and interval estimates of relative hazards of PTD associated with the three pairwise contrasts among the three treatment groups. These estimates, and associated tests of significance, will be obtained using the Cox proportional hazards regression model developed in addressing Aim 1, fully adjusted for potential confounders including depression severity, as described above, via transformed linear contrasts of treatment group associated regression parameters. Based on the results of Aim 1 analyses of dose-response, we will obtain confounder adjusted relative hazards associated with PTD with levels of dose of a given treatment modality

(e.g. antidepressants, <30 days, 30-120 days, > 120 days duration during pregnancy), vs. particular levels of dose of another treatment (e.g. psychotherapy, ≥ 4 visits that has shown to be effective). We would categorize the comparator treatment (e.g., psychotherapy), based on the Aim 1 findings that the effectiveness of the comparator treatment in reducing risk of PTD varied by dose (e.g. no effect for < 4 visits).

As a secondary (exploratory) analysis, we will evaluate the treatment effectiveness separately for those with more severe underlying depression before treatment vs. those with more mild depression. Treating depression may be more beneficial for those with severe depression.

Analyses of LBW as the outcome will parallel those described above for PTD, but logistic regression techniques will be used rather than Cox regression.

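### The LBW dose-response analyses drop the time-dependent handling of dose used for PTD and name no exposure window, so totals to delivery would be cut short by the early births that cause LBW

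*Combined protocol and SAP*

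**What the plan says.** All the text is in section 6.1 of the combined protocol and SAP unless noted.

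- **PTD, Aim 1.** Antidepressant exposure is examined by "dosage of use, duration of the use, and timing of effect (single vs. multiple trimesters), in the context of time-dependent covariates". Psychotherapy is examined by "the number of sessions received) and the effect of timing of treatment, also both as time-dependent covariates". The model is Cox regression.
- **LBW, Aims 1 and 2.** "Analyses of LBW as the outcome will parallel those described above for PTD, but logistic regression techniques will be used rather than Cox regression". The opening of the section confirms it: "Birthweight for all newborns will be obtained from EMR and analyses for LBW will utilize logistic regression".
- **Aim 2 dose levels.** The examples are "antidepressants, <30 days, 30-120 days, > 120 days duration during pregnancy" and "psychotherapy, ≥ 4 visits that has shown to be effective". A dose level of one treatment is set against a dose level of another.
- **Preterm cut-off.** "All pregnancies ending before 37 completed weeks (259 days) will be considered as failure (PTD".
- **Treatment start.** Section 3.1.3 screens women at the first prenatal visit and again at 22-24 weeks. Women already treated before screening form a separate group.

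For the LBW dose analyses, the plan gives no fixed window, landmark, rate per week at risk or other handling of gestational length. Delayed entry and time-dependent covariates are described only for the Cox model. Sections 6.1.1 (propensity score) and 6.1.2 (instrumental variable) deal with which treatment a woman receives, not with how much she accrues.

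**The concern.** In the PTD model a woman's dose counts only up to the gestational age at which she is compared with others still pregnant. Ordinary logistic regression for LBW has one record per birth and no time axis, so that protection is lost and nothing replaces it. Days of use during pregnancy, number of sessions and number of trimesters exposed then read most naturally as totals at delivery. Short gestation limits these totals and is also a main route to low birthweight, so the outcome helps decide the dose category.

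At stake is a dose-response that appears to favour longer treatment when treatment does nothing. Section 8 intends the findings to feed into practice guidelines. A larger sample does not remove the bias; it only makes it more likely to reach significance.

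**Working it through.** The plan states no figure for the LBW dose-response, so there is none to reproduce.

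**1. Arithmetic from the plan's figures.** More than 120 days means at least 121.

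- The last preterm day is 258. Latest start that allows 121 days: 258 − 121 = day 137 (19w4d).
- First treated at the second screen, day 154 to 168: 154 + 121 = day 275 (39w2d) and 168 + 121 = day 289 (41w2d). Such a woman must still be pregnant then to enter the top category, so none of her preterm births can fall in it.
- Same woman, start on day 154, treated to delivery: birth on day 258 gives 258 − 154 = 104 days (middle category); birth on day 280 gives 126 days (top category). Only the date of birth differs.

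**2. Null simulation.** Treatment affects neither gestation nor birthweight. PTD is 8-11% and LBW 5-10%, the ranges in section 6.2.2. Start weeks, stopping rates and the relation of birthweight to gestation are assumptions; 54-70% of LBW births are preterm in these runs. There are 600,000 pregnancies per scenario. Total days to delivery = min(intended course, gestational age − start), entered in logistic regression for LBW. False significance = 1 − Φ(1.96 − |β|/SE) + Φ(−1.96 − |β|/SE), with SE rescaled to the stated number of treated women.

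| Start | Stopping | OR per 30 days | OR >120 vs 30-120 days | False significance, n = 400 | n = 1,600 |
|---|---|---|---|---|---|
| wk 8-24 | none before delivery | 0.41-0.55 | 0.19-0.28 | 97-98% | 100% |
| wk 8-24 | mean 120 days | 0.90-0.93 | 0.53-0.64 | 13-14% | 38-40% |
| wk 8-12 | mean 240 days | 0.92-0.93 | 0.89-0.91 | 16-17% | 47-52% |
| wk 8-12 | mean 120 days | 0.96-0.97 | 0.94 | 7-8% | 15-17% |

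The truth is 1.00 and the nominal error rate 5%. The 1,600 is the effective size per cohort used in section 6.2.2.

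**3. More than 120 versus under 30 days, within treatment.** Separate null runs with random stopping gave 0.61-0.76 for starts over weeks 8-24 or 6-30, and 0.96-0.98 for starts over weeks 8-12.

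**4. Sessions, 4 or more versus fewer.** At PTD 9.5% the null OR was 0.59-0.76 with assumed sessions every 4 weeks and 0.85-0.97 every 2 weeks.

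**5. Aim 2 cross-treatment contrast.** Against 4 or more visits (PTD 9.4%, sessions every 2 or 4 weeks, starts over weeks 8-24 or 6-30), the null OR was 0.69-0.91 for more than 120 days and 1.09-1.63 for 30-120 days. The error runs both ways.

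**6. Does the cause explain the effect?** In the runs of step 2:

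- Time-dependent Cox for PTD gave HR 0.97-1.01 per 30 days. Total duration in a logistic model for PTD gave OR 0.36-0.95. The time-dependent handling is what protects PTD.
- LBW on dose accrued by 24 weeks, among women still pregnant then, gave OR 0.99-1.01 per 30 days. In separate runs, dose accrued by 28 weeks gave 0.98-1.01 for the category contrast.

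**The case against.** The strongest reply is that the plan never says LBW will use totals to delivery. Logistic regression can take other doses, and the remedy below is itself a logistic model. Section 6.1 also names measures that need not accumulate, such as dosage, drug class and, where numbers permit, early-pregnancy dose. That stands: a reader might infer that logistic regression can use only totals, and the documents do not support it. What remains is that duration, sessions and trimesters are named with no window. An analyst following the text would compute totals.

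A reader might also infer a fixed and large bias. The documents do not support that either. Screening begins at the first prenatal visit, so early starts are plausible, and with early start and frequent stopping the bias is nearly nil. Start dates, stopping and session spacing are not given.

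The day categories are examples attached to the Aim 2 cross-treatment contrasts; Aim 1 states no categories. The within-treatment contrast of more than 120 versus under 30 days is therefore illustrative. The cross-treatment contrasts do not lean uniformly toward longer treatment.

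Finally, these analyses supplement the pairwise cohort comparisons on which section 6.2.2 bases power. That limits the importance of the point but does not make the analyses sound: within Aim 2, only the analysis by severity is labelled exploratory.

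**Conclusion.** The point holds for the cumulative LBW measures: duration, number of trimesters exposed and number of sessions. As written, they carry no exposure window, and the natural reading biases the within-treatment LBW dose-response toward apparent protection from longer treatment.

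The direction follows from the plan's own day counts. The size rests on assumptions: OR about 0.6 to 0.76 for more than 120 versus under 30 days when many women start late, about 0.96 to 0.98 when nearly all start at weeks 8 to 12, and a larger bias where treatment usually continues to delivery. Aim 2 cross-treatment LBW dose contrasts can be wrong in either direction.

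It would be tempting to extend this to the main LBW comparisons of Cohorts A, B and C with D. The checks here did not test those, and they are not part of this point. The PTD dose-response is adequately handled. The text should be corrected before analysis, but the primary contrasts do not depend on it.

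**What to change.** In section 6.1, under Aims 1 and 2, replace the parallel-analysis sentence for the cumulative LBW measures with a rule to this effect:

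- Dose is the amount accrued by one prespecified gestational age, the same for antidepressants and psychotherapy, among pregnancies still ongoing at that age.
- Totals to delivery are not used for LBW.
- Day, session and trimester categories are redefined to fit the window.
- The handling of women first treated after that age is stated. The 24-week check used only women who had started by then.

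Both 24 and 28 weeks restored the null in simulation. Adding gestational age at delivery as a covariate is not a substitute, because it conditions on a mediator.

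**Cost.** One derived variable and revised wording, with some loss of information. Dose after the landmark is not used, so the late-pregnancy question is not answered for LBW by this analysis. Births before the landmark drop out (about 0.2-0.4% at 28 weeks in simulation). Long-duration groups shrink: by day 196 (28 weeks), 121 days of use needs a start by 196 − 121 = day 75 (10w5d), and a woman starting at the second screen can have at most 196 − 154 = 42 days. With starts at weeks 8-24, the group above 120 days fell from about 12-48% of treated women to 2-10%, which is why the example categories cannot be kept.
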